2.2 Clinical Hypotheses

[figure not shown]
At least one concurrently dosed combination of AGN-199201 and AGN-190584 will:

- demonstrate a significant improvement in UNVA over monotherapy with AGN-199201 and monotherapy with AGN-190584 when they are dosed at the same concentrations as the combination
- 2. produce safety and tolerability findings no worse than cumulative findings with AGN-199201 monotherapy and AGN-190584 monotherapy when they are dosed at the same concentrations as the combination

3. Study Design

This study is a phase 2, multicenter, double-masked, parallel-group, randomized sequence, dose response, vehicle-controlled study in patients with presbyopia. Four groups (see Table 1) of different concentrations of AGN-190584 will be used to compare unfixed combinations with AGN-199201 and a fixed combination of AGN-190584 and a fixed combination of AGN-190584 and AGN-199201 solutions dosed in the nondominant eye during 5 dosing periods. For all 4 treatment groups, each dosing period will be once daily for 2 consecutive days, followed by a 7 to 21 day washout before the next 2-day dosing period, until exit after the fifth 2-day dosing period. The study duration will be 39 to 112 days per patient.

Following a screening visit (days -18 to -1) patients will be randomized at a baseline visit (visit 1) in a 1:1:1:1 ratio (stratified by the UNVA at baseline of $\leq 20/80$ and > 20/80) to 1 of the following treatment groups (also summarized in Table 1):

All patients will receive the fixed combination of AGN-199201 and AGN-190584 ophthalmic solutions within one of the 5 dosing periods. Vehicles for AGN-190584, AGN-199201, and the fixed combination ophthalmic solutions all have the same formulation.

Study medication will be administered once daily in each eye during office visits at hour 0 (8 AM \pm 1 hour) for 2 consecutive days during each dosing period. Dosing periods will be separated by a washout period of 14 ± 7 days. Eyes receiving both AGN-199201 and AGN-190584 are to receive a single drop of AGN-199201, followed approximately 5 to 7 minutes later by a single drop of AGN-190584. Eyes receiving the fixed combination of AGN-190584 and AGN-199201 are to receive a single drop of the fixed combination drug, followed approximately 5 to 7 minutes later by a single drop of vehicle. Eyes receiving vehicle alone are to receive 2 drops of vehicle, separated by approximately 5 to 7 minutes. The study design is depicted in Figure 1.

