9.1 Definitions

9.1.1 Adverse Event

An adverse event is any untoward medical occurrence in a patient or clinical investigation patient administered a pharmaceutical product and that does not necessarily have a causal relationship with this treatment. An adverse event can therefore be any unfavorable and unintended sign (including an abnormal laboratory finding), symptom, or disease temporally associated with the use of a medicinal (investigational) product, whether or not related to the medicinal (investigational) product. In addition, during the screening period, adverse events will be assessed regardless of the administration of a pharmaceutical product.

Note: Adverse events must be collected once informed consent has been obtained, regardless of whether or not the patient has been administered study drug.

Progression of treatment indication including new or worsening of anticipated clinical signs or symptoms, which are collected as clinical efficacy variables and assessed as unequivocally associated with the disease progression and /or lack of efficacy, should NOT be reported as adverse events unless the disease progression is greater than anticipated in the natural course of the disease.

Adverse events will be assessed, documented, and recorded in the electronic case report form (eCRF) throughout the study (ie, after informed consent has been obtained). At each visit, the investigator will begin by querying for adverse events by asking each patient a general,

non-directed question such as "How have you been feeling since the last visit?" Directed questioning and examination will then be done as appropriate. All reported adverse events will be documented on the appropriate case report form.

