9.3 Procedures for Reporting a Serious Adverse Event

Any serious adverse event occurring during the study period (beginning with informed consent) and for at least 28 days after the last dose of study drug must be immediately reported but no later than 24 hours after learning of a serious adverse event. Serious adverse events must be reported to Allergan (or Agent of Allergan as listed on the Allergan Study Contacts Page and recorded on the serious adverse event form. All patients with a serious adverse event must be followed up and the outcomes reported. The investigator must supply the sponsor and the IRB/IEC with any additional requested information (eg, autopsy reports and discharge summaries).

In the event of a serious adverse event, the investigator must:

- 1. Notify Allergan immediately by fax or email using the serious adverse event form (contact details can be found on page 1 of the serious adverse event form); phone numbers and relevant Allergan personnel contacts are also on the front page of protocol and Study Contacts Page.
- 2. Obtain and maintain in his/her files all pertinent medical records, information, and medical judgments from colleagues who assisted in the treatment and follow-up of the patient.
- 3. Provide Allergan with a complete, written description of the adverse event(s) on the serious adverse event form describing the event chronologically, including any

treatment given (eg, medications administered, procedures performed) for the adverse event(s). Summarize relevant clinical information about the event: signs, symptoms, diagnosis, clinical course and relevant clinical laboratory tests, etc. Include any additional or alternative explanation(s) for the causality which includes a statement as to whether the event was or was not related to the use of the investigational drug.

4. Promptly inform the governing IRB/IEC of the serious adverse event as required by the IRB/IEC, local regulations, and the governing health authorities.

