**Table 5-23 AE Terms**

Term	Description
Treatment-emergent	An event that initially occurs or increases in intensity on or after the treatment start date, where: 

• Treatment start date <math>\leq</math> event start date <math>\leq</math> following washout period before the next 2-day dosing period or last dose date + 30 days

On-therapy	An event where: 

• Treatment start date <math>\leq</math> event start date <math>\leq</math> following washout period before the next 2-day dosing period or last dose date + 30 days

[figure not shown]
AEs, encompassing abnormalities and surgeries reported as occurring after the Screening Visit, will be coded using MedDRA version 19.0 or newer. Unique subjects reporting AEs in the

following AE categories will be summarized by treatment group and overall for the Safety Population as follows:

[figure not shown]

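### New non-serious adverse events are not solicited after the last dose, yet the SAP counts events to 30 days after it, so period 5 is observed for less time than periods 1 to 4

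*SAP*

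**What the plan says.** **Schedule.** Protocol Section 3 (Study Design) states: "Following a screening visit (days -18 to -1) patients will be randomized at a baseline visit". Dosing then takes two days per period, with one dose a day, and each period is "followed by a 7 to 21 day washout before the next 2-day dosing period, until exit after the fifth 2-day dosing period". The total is given directly: "The study duration will be 39 to 112 days per patient". Section 8.9 makes visit 2 of a period the exit visit. A patient who withdraws has the exit procedures at whichever visit turns out to be the last one attended.

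**Collection.** Section 9.1.1 has adverse events recorded from consent for as long as the study lasts, and names no interval after exit. Its routine prompt, an open question on how the patient has felt, is tied to visits: "At each visit, the investigator will begin by querying for adverse events by asking each patient a general". Section 9.2 requires appropriate follow-up of events still ongoing at exit. Section 9.3 extends collection for serious events only, "for at least 28 days after the last dose of study drug must be immediately reported".

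**Analysis.** SAP Table 5-23 gives treatment-emergent and on-therapy events the same upper limit: "following washout period before the next 2-day dosing period or last dose date + 30 days". SAP Table 5-21 lists the timing of every adverse-event summary as Treatment Period and Follow-up, and the readable text does not define Follow-up. SAP 5.1.1.1.6 summarises ocular events per eye and nonocular events per patient, in each case for each dosing group within each dosing period.

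**The concern.** An event that starts in the washout after periods 1 to 4 is caught by the general question at the next period's first visit. The equivalent event after period 5 has no later visit at which to be asked about, although Table 5-23 would classify it as treatment-emergent for up to 30 days. The analysis window and the collection schedule therefore differ in a way that depends on the period.

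Two things are at stake. First, in tables by dosing period, a lower rate of non-serious events in period 5 could reflect less asking and be misread as an order effect or growing tolerance. Second, the second clinical hypothesis (Protocol 2.2) is about safety and tolerability of the combination against the two monotherapies, and these tables are its evidence. Early discontinuation raises the same question for the last treatment received. Protocol 1.4 anticipates that the higher pilocarpine concentration may increase discontinuation.

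**Working it through.** **Inputs** (Protocol Section 3 unless noted): screening 1 to 18 days; 5 periods of 2 dosing days; 4 washouts of 7 to 21 days (midpoint 14); post-dose limits of at least 28 days for serious events (Protocol 9.3) and 30 days in the analysis (SAP Table 5-23).

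**Step 1: reproduce the stated duration.** Duration = screening + 5 × 2 + 4 × washout + f, where f is the number of scheduled days after the last dose.

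- Minimum: 1 + 10 + 28 + f = 39 + f
- Maximum: 18 + 10 + 84 + f = 112 + f

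| Assumed f | Minimum | Maximum | Matches 39 to 112? |
|---|---|---|---|
| 0 | 39 | 112 | yes |
| 1 | 40 | 113 | no |
| 7 | 46 | 119 | no |
| 28 | 67 | 140 | no |
| 30 | 69 | 142 | no |
| fifth washout (7 to 21) | 46 | 133 | no |

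Only f = 0 fits. The amendment history agrees. The superseded 44 to 117 days equals 1 + 15 + 28 and 18 + 15 + 84, that is, five 3-day periods and again nothing after the last one.

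**Step 2: observation of new non-serious events, counted from a period's first dose.**

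- Periods 1 to 4: 2 + 7 = 9, 2 + 14 = 16 and 2 + 21 = 23 days, closed by the next visit.
- Period 5, nominal (Table 5-23): 2 + 30 = 32 days.
- Period 5, scheduled: 2 + 0 = 2 days.
- Scheduled period 5 relative to periods 1 to 4: 2/9 = 22.2%, 2/16 = 12.5%, 2/23 = 8.7%.
- Nominal period 5 relative to periods 1 to 4: 32/9 = 3.6, 32/16 = 2.0, 32/23 = 1.4.

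So the nominal period-5 window is longer than the others, while the scheduled one is much shorter.

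**Step 3: serious events.** Guaranteed collection covers 28 of the 30 days (93%), leaving 2 days that are counted but not guaranteed.

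**Step 4: effect on comparisons between treatments.** Protocol 7.5 gives 5 sequences of 8 patients per group. *Assume* that each treatment falls last in exactly one sequence (the sequence table is not readable). Then 8/40 = 20% of each treatment's exposures within a group fall in period 5, or 32 of 160 for the fixed combination. With the midpoint washout, each treatment keeps (4 × 16 + 2)/(5 × 16) = 66/80 = 82.5% of the observation time it would have had with five equal periods (84.4% with 7-day washouts, 81.7% with 21-day washouts). Under this assumption the fraction is the same for every treatment. The shortfall then lowers the level in treatment tables but hardly the contrasts, and shows mainly in tables by period.

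**The case against.** **Follow-up does exist.** A reader might infer that nothing is collected after the last dose. The protocol does not support that: serious events run to at least 28 days and events ongoing at exit are followed. Section 8.5 also tells patients to report changes in condition, so spontaneous reports are possible. What stands is narrower: new non-serious events that begin after exit are not asked for.

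**The final dose may be followed by a query.** Because Section 9.1.1 puts the general question at the start of a visit, one might conclude that nobody asks after the final dose. This cannot be shown. The same section goes on to directed questioning and examination, efficacy assessments run to hour 10, and the readable text omits the visit details of Section 8.4 and the protocol's schedule table. SAP 4.3 is also unreadable, so it cannot be said that the schedule lacks a Follow-up entry. Against a later contact there is only the day count, though that count is exact.

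**Table 5-23 classifies events.** It decides which reported events count and does not assert that every patient was observed to day 30. That is correct, and it is why the definition can stay. A percentage by period is still hard to read when the time over which events were solicited differs this much.

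**Discontinuers do not clearly gain time.** The nominal post-dose windows, 30 days against 21 to 7, give ratios of 1.4 to 4.3, which tempts one to claim a bias against treatments that cause discontinuation. Those ratios compare nominal limits. Exit procedures take place at the last visit attended, so the time actually observed may be shorter than in a patient who continues.

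**Late events may be few.** Protocol 1.3 and 1.4 describe a short effect: maximal miosis at about 1 hour, and pilocarpine's effect on near vision mostly gone by 6 hours. The documents give no share of events that start after the second dosing day, so no understatement of incidence can be calculated from them.

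**Conclusion.** The collection schedule and the analysis window do not match. For new non-serious events, tables by dosing period compare 2 scheduled days in period 5 (nominally 32) with 9 to 23 days in periods 1 to 4. An early discontinuer likewise has no scheduled collection of such events after the last visit attended. For serious events the gap is at most 2 days of guaranteed reporting. This rests on the stated duration being complete and on Section 8.4 containing no contact outside it.

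Bias between treatments among completers is probably small if the sequences are balanced. Early discontinuation is not balanced by design, but the direction of its effect is not established. The point matters for safety capture and for comparing periods, and does not invalidate the treatment comparisons.

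**What to change.** 1. **Protocol Sections 3 and 9.1.1.** Add one telephone adverse-event contact after the last dose, for completers and early discontinuers. Time it either to the between-period interval or to the end of the serious-event or treatment-emergent window. Restate the duration: a contact at 7 to 21 days gives 46 to 133 days, at day 28 gives 67 to 140, and at day 30 gives 69 to 142. The cost is one call per patient, about 160 in all, by existing site staff.

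2. **SAP adverse-event section.** Keep the Table 5-23 definition for the main tables. Add one supplementary table, by treatment and by period, using a window of equal length: onset on the two dosing days of each period. Show washout and post-exit events separately. If Section 8.4 does not already provide it, ask about adverse events at the end of the final dosing-day visit; otherwise events that start late on that day are solicited after periods 1 to 4 but not after period 5. The cost is one table and, at most, one question.

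3. **Both documents.** Align the exit, 28-day and 30-day end points, state when collection of non-serious events stops, and define Follow-up in SAP Table 5-21. This changes text only.

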**Table 5-21 AE Summaries**

[figure not shown]
Endpoint	Description	Timing	Methodology
Overall summary	Overall summary only for the following categories: 
 
• Treatment-emergent AEs (TEAEs)
 
• Treatment-related TEAEs
 
• Study-procedure-related TEAEs
 
• On-therapy serious adverse events (SAEs)
 
• On-therapy fatal SAEs
 
• AEs leading to discontinuation
 
	Treatment Period, Follow-up	Categorical descriptives
TEAEs	Overall summary and by SOC and PT	Treatment Period, Follow-up	Categorical descriptives
Common TEAEs	Summary by PT 
 
• Includes TEAEs occurring in <math>\geq</math> 5.0% of subjects in any treatment group
 
	Treatment Period, Follow-up	Categorical descriptives
TEAEs by intensity	Overall summary and by SOC, PT, and intensity 
 
• Subjects categorized overall and within each SOC and PT for the most intense occurrence
 
	Treatment Period, Follow-up	Categorical descriptives
Treatment-related TEAEs	Overall summary and by PT	Treatment Period, Follow-up	Categorical descriptives
Study-procedure-related TEAEs	Overall summary and by PT	Treatment Period, Follow-up	Categorical descriptives
On-therapy SAEs 	Overall summary and by PT	Treatment Period, Follow-up	Categorical descriptives
On-therapy fatal SAEs 	Overall summary and by PT	Treatment Period, Follow-up	Categorical descriptives
AEs leading to study discontinuation 	Overall summary and by PT	Treatment Period, Follow-up	Categorical descriptives

[figure not shown]
 Subjects who report  $\geq$  1 AE in the AE category and all AEs for those subjects will be listed. SOCs will be sorted alphabetically; PTs will be sorted in descending frequency in the highest dose group.

### **5.1.1.5 Subgroup Analyses**

Subgroup analyses will be performed for the primary efficacy variable by UNVA severity at baseline and iris color (brown or not brown).

### **5.1.1.6 Interim Analyses**

Not applicable.

## **5.1.2 Determination of Sample Size**

The study consists of 4 parallel groups and forty patients per each parallel group will be enrolled. With a 1:1:1:1 parallel group allocation and 10% dropout rate, a total of 160 patients are to be enrolled in order to have 144 patients complete the study. The sample size is deemed appropriate to assesses the efficacy profile of the combination relative to monotherapies.

## **5.2 Changes in the Conduct of the Study or Planned Analyses**

### **5.2.1 Changes in the Conduct of the Study**

Not applicable.

### **5.2.2 Changes to Analyses Prior to Database Lock**

The term of ‘average change from baseline in UNVA letters’ instead of ‘weighted average change from baseline in UNVA letters’ will be used since weighted average concept only applies when missing mid-timepoint values are imputed. UNVA responder analyses with at least a 2-line improvement in mesopic, high contrast UNVA from baseline at a majority of postdose timepoints (6 or more) in the nondominant eye will be added.

Subgroup analyses by gender, race and ethnicity will be performed .

mITT definition will be change to ‘All randomized subjects with a baseline and at least 1 post baseline assessment of mesopic high contrast UNVA, with baseline vary not more than 3 lines across the 5 dosing period, and will be analyzed as randomized.’

## **6. Data Handling and Analysis Conventions**

### **6.1 Study Treatment Conventions**

#### **6.1.1 Analysis Days**

[figure not shown]
Treatments are defined as follows:

**Table 6-1**                      **Analysis Day Definitions**

Term	Description
Treatment Day	Relative to treatment start date If analysis date $\geq$ treatment start date: 

• Day = analysis date – treatment start date + 1

○ Day 1 = treatment start date

### **6.1.2**                      **Missing/Incomplete Treatment End Date**

If the investigator is unable to provide the treatment end date, treatment end date will be imputed to the last available dosing record date/last available efficacy assessment date.

█ [REDACTED]

█ [REDACTED]

█ [REDACTED]

### 6.3 Site Pooling

Data from all sites will be pooled for analysis.

### 6.4 Missing/Incomplete Date Conventions

Dates may be imputed with year, month, and day values under certain scenarios:

**Table 6-4 Imputation Scenarios**

Scenario	Complete			Imputable
	Year	Month	Day	
1	Yes	Yes	Yes	Complete
2	Yes	Yes	—	Yes
3	Yes	—	Yes	No 
4	Yes	—	—	Yes
5	—	Yes	Yes	No 
6	—	Yes	—	No 
7	—	—	Yes	No 
8	—	—	—	Yes

 Not allowed per database design.

Dates will be imputed initially toward a specified target date for imputable scenarios 2, 4, and 8, and adjusted against the latest reasonable dates. The initial imputed date is determined by the following algorithm:

**Table 6-5 Initial Imputed Date Algorithm**

Available Year (YYYY)	Available Month (MM)			
	Missing	< Target Month	= Target Month	> Target Month
Missing	Target Date	—		
< Target Year	YYYY-12-31	YYYY-MM-LD		
= Target Year	Target Date	YYYY-MM-LD	Target Date	YYYY-MM-01
> Target Year	YYYY-01-01	YYYY-MM-01		

YYYY = available start date year; MM = available start date month; LD = last day of the month.

#### 6.4.1 Missing/Incomplete AE Start Date

AE start dates will be imputed as the minimum of the following:

- Initial imputed date, where target date = Treatment start date
- Complete end date

## 6.4.2 Missing/Incomplete Medication Start Date

Medication start dates will be imputed as the minimum of the following:

- Initial imputed date, where target date = Treatment start date – 1
- Complete end date

## 6.4.3 Missing/Incomplete AE/Medication End Date

AE and medication end dates will be imputed as the minimum of the following:

- Initial imputed date, where target date = Treatment end date + 30
- Death date

## 6.5 Efficacy Endpoint Conventions

Not applicable.

## 6.6 Safety Endpoint Conventions

### 6.6.1 Adverse Events

#### 6.6.1.1 Missing Intensity or Relationship

If the investigator is unable to provide the actual values, the following imputations will be applied:

**Table 6-6 Missing AE Intensity and Relationship Imputation Algorithms**

Missing Value	Imputation	Timing
Intensity	Mild	Screening Period, Pretreatment Period
	Severe	Treatment Period
Relationship	—	Screening Period, Pretreatment Period
	Related	Treatment Period

#### 6.6.1.2 Possible Distant Spread of Toxin (PDSOT)

[figure not shown]
Not applicable.

#### 6.6.1.3 AE Group of Interest

Not applicable.

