Safety measures will be analyzed using the safety population. Medical Dictionary for Regulatory Activities (MedDRA) nomenclature will be used to code adverse events. Incidence rates of each treatment-emergent adverse event will be summarized by primary system organ class and preferred term. Treatment-emergent adverse events are events that occur or worsen after the treatment. Summary tables will be generated for all treatment-emergent adverse events regardless of causality as well as for those considered to be treatment-related. The adverse events will be classified into ocular and nonocular types and will be summarized separately as described below. Ocular adverse events and other ocular evaluations will be summarized using eye as the experimental unit by dosing group and dosing period. Nonocular adverse events and other nonocular assessments (eg, vital signs) will be summarized using patient as the experimental unit by dosing group and dosing period.

Detailed descriptions of the safety analyses for adverse events and other safety measures will be documented in analysis plan.

Sample Size Calculation:

The study consists of 4 parallel groups and 5 sequences of 2-day dosing periods within each group (see Figure 1). Each dosing period is separated by a washout of 14 ± 7 days and each sequence is tested 8 times resulting in 40 patients per group.

The sample size is deemed appropriate to build a response surface model that assesses the efficacy profile of the combination relative to monotherapies.

1. Background and Clinical Rationale

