Pilocarpine is a muscarinic receptor agonist that mimics the actions of the parasympathetic neurotransmitter, acetylcholine, on smooth muscle. This causes 2 effects which enhance near vision: 1) constriction of the iris sphincter muscle, resulting in pupil miosis, and 2) constriction of the ciliary muscle, resulting in central lens steepening and lens accommodation (focusing from distance to near) in humans (as well as in animal models) (García-Lázaro et al, 2012). Reducing the pupil size has long been recognized as an effective way to increase the useful depth of focus, in part by reducing peripheral aberrations (Tucker and Charman, 1975). The current use of pilocarpine ophthalmic solution monotherapy for the treatment of presbyopia is limited by the commonly experienced adverse event of temporal and periorbital headache (ie, brow ache), which is believed to be due to the strength of the ciliary muscle contraction (Tsai and Forbes, 2009). The side effects of pilocarpine monotherapy for treatment of glaucoma can be intolerable due to headache and visual disturbances (blurred vision and visual impairment described as dim, dark or jumping vision), resulting in a discontinuation rate of approximately 20% to 25% (NDA 200-890; Tsai and Forbes, 2009).

Oxymetazoline hydrochloride (HCl) is currently approved by the US FDA as over-the-counter (OTC) eye drops, under the brand names Visine[®] LR and Ocuclear[®], at a concentration of 0.025% for topical (ocular) administration for the relief of redness of the eye due to minor eye irritations. It is also available as an OTC nasal spray under the brand name Afrin[®] at a concentration of 0.05% for topical (intranasal) administration for temporary relief of nasal congestion, sinus congestion and pressure, and to shrink swollen nasal membranes.

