1.3 Clinical Summary

Four pilot clinical studies designed to evaluate the safety and efficacy of different combinations of topical pilocarpine and oxymetazoline ophthalmic solutions for the treatment of presbyopia and hyperopia were conducted between 2011 and 2013 by AltaVista Instituto del Investigation Medica at the clinic of [name] ([name], 2013). The concentration of pilocarpine tested in all 4 studies was 1.0%, while the concentrations of oxymetazoline tested ranged from 0.0125% to 0.125%. Dosing frequency ranged from a single drop to 1 drop 3 times daily for 6 months. In the clinical data reported by AltaVista, topical ocular dosing of a fixed combination of pilocarpine and oxymetazoline solutions in patients resulted in no serious adverse events. In a study of 65 patients who used a fixed combination of pilocarpine 1.0% and oxymetazoline 0.0125% up to 3 times daily for 6 months, 3 patients (4.6%) discontinued use of the drops due to brow ache or ocular pain ([name], 2013). This incidence is much lower than the reported 20% to 25% discontinuation rate with pilocarpine monotherapy for glaucoma and suggests that the administration of oxymetazoline with pilocarpine may improve the tolerability profile relative to pilocarpine monotherapy (NDA 200-890; Tsai and Forbes, 2009). Minor, infrequent adverse events were also reported, including a sense of decreased illumination and ocular floaters. AltaVista also reported that oxymetazoline prolonged the duration of the pilocarpine-induced improvement in UNVA from approximately 4 to 6 hours, with the greatest difference (approximately 1 line) between the combination and pilocarpine monotherapy observed at 6 hours after dosing.

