#### 5.1.1.1.6 Other Common Conventions

Ocular adverse events and other ocular evaluations will be summarized using eye as the experimental unit by dosing group and dosing period. Nonocular adverse events and other nonocular assessments will be summarized using patient as the experimental unit by dosing group and dosing period.

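### With no adverse-event group of interest defined, pilocarpine's headache, brow-ache and ocular-pain reaction may be scattered over tables that do not add up to patients affected

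*SAP*

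**What the plan says.** - SAP 6.6.1.3, headed "6.6.1.3 AE Group of Interest", reads not applicable. The entry is not redacted.
- SAP Table 5-21 tabulates treatment-emergent events overall, by system organ class and PT, by PT and by worst intensity, all as categorical descriptives. Its common-event table "Includes TEAEs occurring in" at least 5.0% of subjects in any treatment group, PT by PT.
- Protocol Summary, Safety: "The adverse events will be classified into ocular and nonocular types and will be summarized separately as described below". SAP 5.1.1.1.6 sets the unit: "Ocular adverse events and other ocular evaluations will be summarized using eye as the experimental unit by dosing group and dosing period". Nonocular events use the patient.
- Protocol 1.1 says pilocarpine monotherapy for presbyopia is limited by the "commonly experienced adverse event of temporal and periorbital headache (ie, brow ache"). Protocol 1.3 reports that in a 65-patient pilot of the fixed combination, 3 patients (4.6%) "discontinued use of the drops due to brow ache or ocular pain".
- Protocol 1.3 and 1.4 say that a larger sample, or higher pilocarpine strengths, may be needed to test that tolerability finding properly.
- Protocol 2.2, second hypothesis: at least one combination will "produce safety and tolerability findings no worse than cumulative findings with AGN-199201 monotherapy and AGN-190584 monotherapy" at matching concentrations.

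**The concern.** The protocol identifies one reaction as pilocarpine's limiting problem, and the pilot counted it as a single thing: patients with brow ache or ocular pain. The visible tables do not reproduce that count. Brow ache, which the protocol describes as a headache, may be classed as nonocular and ocular pain as ocular. The two would then sit in different tables with different units. A patient reporting both appears in both, so adding rows double-counts. With about 36 to 40 patients on each unfixed treatment, a real difference could be spread over rows of one or two patients and be read as no difference. A grouping chosen after unmasking to repair this would be open to the charge of selection.

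**Working it through.** **Numbers of patients.** Protocol 7.5: 8 × 5 = 40 per group, and 4 × 40 = 160. Protocol 4.1: 40 × (1 − 0.125) = 35 completers per group. SAP 5.1.2: 160 × (1 − 0.10) = 144, and 144 / 4 = 36 per group. The three active pilocarpine groups give 3 × 36 = 108 patients (3 × 35 = 105 at the protocol's dropout rate). Each such patient also has a period on AGN-199201 vehicle, so combination against pilocarpine alone is a within-patient comparison.

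**Assumptions, not in the documents.** Event rates are 15% on pilocarpine alone and 5% on one combination, with 10% v 3% and 20% v 5% as a range. The documents give only discontinuation rates from other settings (20% to 25%, and 4.6%). The share of events coded to each PT is also assumed.

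**Model.** P(event | b) = Φ(a + b), with b ~ N(0, 1) shared by a patient's two periods and a = √2 · Φ⁻¹(rate), so that the average rate is as assumed. The comparison is the exact McNemar test at two-sided 0.05, counted when it favours the combination. This test only measures resolution; the SAP plans no such test.

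**108 pooled patients, 15% v 5%.** Expected events are 108 × 0.15 = 16.2 and 108 × 0.05 = 5.4, times the PT's share.

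| What is compared | Expected events | Detected |
|---|---|---|
| Grouped term | 16.2 v 5.4 | about 74% |
| One PT with 90% of events | 14.6 v 4.9 | about 66% |
| One PT with 80% | 13.0 v 4.3 | about 57% |
| One PT with 60% | 9.7 v 3.2 | about 40% |
| Each of three equal PTs | 5.4 v 1.8 | about 15% |

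With three equal PTs, at least one shows the difference in 39% of runs. For 10% v 3% the figures are 54% grouped and 18% for any of three equal PTs. For 20% v 5% they are 96% and 74%.

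**One pilocarpine concentration, 36 patients, grouped term.** Expected events are 36 × 0.15 = 5.4 and 36 × 0.05 = 1.8, the same counts as one of three equal PTs in 108. Detection is about 16% (about 5% at 10% v 3%; 38% to 40% at 20% v 5%). The reason can be checked by hand: 2 × 0.5⁵ = 0.0625 and 2 × 0.5⁶ = 0.031, so at least six discordant patients, all in one direction, are needed.

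**Common-event table.** 5% of 36 is 1.8 and 5% of 40 is 2.0, so a PT needs two patients. At a 10% rate in 40 patients, a single term qualifies with probability 1 − 0.9⁴⁰ − 40 × 0.1 × 0.9³⁹ = 0.92. Each of three equal PTs (rate 3.3%) qualifies with probability 0.39. In 36 patients, the chance that none of the three qualifies is 28%.

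**The case against.** - **The split is unproven.** Neither document shows PT coding, and Protocol 1.1 treats periorbital headache and brow ache as one symptom. A reader might infer that the reaction is split and that most of the resolution is lost. The documents support only that it may be split; if one PT takes 90% of events, the loss is modest (74% to 66%).
- **No planned test loses power.** This stands. The visible tables are descriptive, and grouping PTs supplies neither a margin nor a test for the second hypothesis.
- **A headache scale may exist.** Study 199201-007 used a visual analogue scale (VAS) for temporal and supraorbital headache, and both abbreviation lists include VAS. Redacted safety sections may hold such an analysis, so it cannot be said that headache is ignored. A headache score would still not count patients affected or cover ocular pain.
- **Patient-level counts partly exist.** SAP 5.1.1.4.2 counts unique subjects, and Table 5-21 lists all events of patients with an event leading to discontinuation. Discontinuations for this reaction can be recovered from that listing. The overall rows count each patient once, but for all events together.
- **The entry may be a template line.** It follows a heading on spread of toxin, also marked not applicable, so it need not be a considered refusal. The effect on the tables is the same.
- **The rates may be too high.** Study 199201-007 found no meaningful difference in adverse events apart from eyelid retraction, and dosing here is two single daily doses per period. This limits the expected yield. Protocol 1.3 and 1.4 nevertheless say the tolerability question still needs a proper test.

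**Conclusion.** The point holds as a cheap improvement. No grouped term is defined, and the pilot's own measure, patients with brow ache or ocular pain, cannot be read from the visible planned tables. That conclusion needs no power figure. The possible loss of resolution runs from modest (74% to 66%) to severe (74% to 15% for a given PT). It rests on assumed rates, a within-patient correlation that the documents do not give, and an unknown split. A reader might also infer that grouping would settle the question at each pilocarpine concentration. It would not: about 36 patients detect 15% v 5% only about 16% of the time, so the comparison has to be pooled.

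**What to change.** Replace the entry in SAP 6.6.1.3 with one group: all PTs for headache, brow ache, temporal, supraorbital or periorbital pain, and eye or ocular pain. Fix the PT list under masking before database lock.

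- Count each patient once per treatment, across ocular and nonocular events.
- Tabulate incidence, worst intensity and discontinuation by treatment.
- Give the within-patient difference between combination and pilocarpine alone at the same concentration, with a 95% confidence interval, pooled over the three active pilocarpine concentrations. Show per-concentration results descriptively.
- Keep the PT tables, and present the group beside any headache VAS in the redacted sections.

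The cost is SAP wording, an agreed PT list and one extra table from data already collected. The downside is that the group mixes incidental headache with pilocarpine-type pain; the retained PT tables let a reader see how much.
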